Relationship between attention and emotional function after traumatic brain injury (TBI): probing neural circuitry with transcranial direct current stimulation (tDCS)

I. PURPOSE OF THE STUDY AND BACKGROUND

1. Purpose of the study

The purpose of this pilot study is to investigate the relationship between attention and emotional function post-TBI in an effort to better understand the cognitive mechanisms of emotional processing in patients with TBI, and explore novel treatment strategies to improve emotional regulation using tDCS to modulate activity in the dysfunctional prefrontal-limbic circuits. This project will provide pilot data for extramural funding to expand on this topic.

The specific aims are:

1) To examine the relationship between alerting, orienting and executive attention and emotional recognition, reactivity and regulation in patients with TBI and controls.

Hypothesis: Patients with TBI will show clear patterns of attentional and emotional impairment compared with controls. Deficits in executive attention will be related to deficits in emotional appraisal in patients.

2) To determine whether anodal tDCS applied over the dorsolateral prefrontal cortex in conjunction with computer assisted cognitive re-training of attention will lead to greater improvement in attention and/or emotional regulation compared with sham-tDCS + cognitive re-training. Hypothesis: Patients receiving tDCS + cognitive re-training will show greater improvement in post-intervention measures of attention and emotional regulation.

3) To determine whether resting-state activation patterns in the fronto-limbic connections of patients receiving tDCS + cognitive re-training show greater improvement compared with sham-tDCS + cognitive re-training, using functional connectivity MRI (fMRI).

Hypothesis: Patients receiving tDCS + cognitive re-training will show higher temporal correlation between the frontal and limbic areas compared to baseline than patients receiving sham tDCS + cognitive re-training.

2. Background and Significance

2.1 Cognitive, emotional and behavioral sequelae of Traumatic Brain Injury (TBI)

According to the CDC/National Center for Injury Prevention and Control, approximately 1.4 million individuals sustain a TBI annually in the United States, of which 235,000 are hospitalized and a large proportion become long-term survivors (Brown, Elovic et al. 2008). Key behavioral disturbances that impact life after TBI include inattention, impulsivity, unawareness of problems, apathy, interpersonal difficulties, communication problems, somatic difficulties, and difficulty with emotional adjustment (Kolitz, Vanderploeg et al. 2003). The mechanisms of these behavioral difficulties and the interrelationships between them are not fully understood, but are crucial for planning appropriate treatments to improve quality of life and reduce the societal burden of TBI. Cognitive disturbances following TBI have been shown to occur in the domains of attention, memory, and other aspects of executive functioning, and patients usually undergo

detailed neuropsychological testing to define the extent of these deficits (Brown, Elovic et al. 2008). However, one recent study examined subjective and objective reports of cognitive and behavioral problems in fifty-four individuals 10 years after TBI and found no strong relationships between subjective reports of cognitive problems and test performances; much stronger relationships were found between subjective reports of cognitive change and emotional state (Draper and Ponsford 2009). The results suggest that improved understanding of the interaction between aspects of cognition and emotion is needed to understand and treat behavioral disturbances post-TBI.

Accurate interpretation of emotion in oneself and others is critical for the successful negotiation of social interactions. Several studies have found that a significant proportion of individuals with TBI are unable to recognize and understand affective information from the face, voice, bodily movement, and posture of others, suggesting that they are impaired in emotional appraisal (Bornhofen and McDonald 2008; McDonald, Bornhofen et al. 2009). Lack of response to emotional stimuli is more prevalent for negative emotions, which may further accentuate the impact of the emotional processing deficit in social situations and contribute significantly to the behavioral dysfunction (Saunders, McDonald et al. 2006). In fact, difficulty identifying emotions has been associated with poorer quality of life, even when depression and anxiety are controlled for, and has also been uniquely associated with executive function deficits (Henry, Phillips et al. 2006).

It has also been suggested that the inability to recognize emotions may be related to deficits in error processing during sustained attention to response tasks (O'Keeffe, Dockree et al. 2004), even when controlled for severity of injury (McAvinue, O'Keeffe et al. 2005). Error feedback has been shown to lead to improvement in emotional recognition (McAvinue, O'Keeffe et al. 2005), but training in focused attention and mimicry have not (McDonald, Bornhofen et al. 2009). One recent study in a group of healthy volunteers found that individuals who had difficulty understanding, processing, or describing emotions (alexithymics) on the Toronto Alexithymia Scale (TAS-20) showed less efficient voluntary control of executive attention (Gu, Liu et al. 2008). Elucidating the relationships between specific aspects of attention and emotional processing inform the development of more effective, clinically translatable treatment strategies for behavioral dysfunction post-TBI.

Behavioral assessments have been used to quantify neurobehavioral outcomes in TBI, among which the Neurobehavioral Rating Scale-Revised (NRS-R) has shown subsets of symptoms that tend to present together (Vanier, Mazaux et al. 2000; McCauley, Levin et al. 2001). These subsets support two broadly defined clinical profiles in TBI (Zappala, Thiebaut de Schotten et al. 2012) - disinhibition, difficulty coping, and social inappropriateness arising from damage to the orbitofrontal networks of the prefrontal cortex (PFC) (Berlin, Rolls et al. 2004; Beer, John et al. 2006); and disinterested, unmotivated pseudo-depression arising from damage to the ventromedial networks of the PFC (Shamay-Tsoory, Tomer et al. 2003; Hornak, O'Doherty et al. 2004; Jorge, Robinson et al. 2004; Leopold, Krueger et al. 2011). The PFC is a crucial region for sophisticated information processing involved in social cognition and emotional intelligence (Forbes and Grafman 2010), and is particularly vulnerable to diffuse axonal injury (DAI) in TBI. While symptom classification with the NRS-R supports this paradigm, there is a gap in our understanding of mechanisms of emotional dysfunction after TBI to link recurrent patterns of behavioral symptoms to specific treatments.

2.2 Diffuse Axonal Injury (DAI) leads to shearing of limbic-prefrontal circuits

TBI is caused by rapid acceleration-deceleration of the brain inside the skull, which causes DAI, or disruption of axonal connections between widespread regions of the brain. However, the extent of DAI is difficult to quantify (Inglese, Makani et al. 2005) as it requires sophisticated imaging techniques that are not widely available (Cohen, Inglese et al. 2007). Realistic in vivo and in vitro models of TBI have been able to demonstrate that DAI, marked by bead-like pattern of beta-amyloid precursor protein (beta-APP) in damaged axons, leads to early degeneration particularly in axons of the cingulum bundle and external capsule leading to disconnection between the cortical and thalamic neurons with delayed apoptotic death in the nuclei of the limbic cortex, the seat of emotions (Dikranian, Cohen et al. 2008; Kilbourne, Kuehn et al. 2009). Similarly, a functional magnetic resonance imaging (fMRI) study that compared patterns of cortical activation in patients with cognitive impairment after TBI and controls during a Stroop task, showed that TBI patients showed decreased activity in the anterior cingulate cortex which may reflect cortical disinhibition attributable to disconnection or compensation for an inefficient cognitive process (Soeda, Nakashima et al. 2005). Many of the behavioral symptoms of TBI such as prominent impulsivity, affective instability, disinhibition, difficulties with substance use, sexual expression, and aggression (McAllister 1992) stem from perseverative behavior that can be explained by damage to the prefrontal cortex and/or disconnection between limbic and prefrontal circuits (Morgan, Romanski et al. 1993; Neave, Nagle et al. 1997; Sotres-Bayon, Cain et al. 2006; Hartley and Phelps 2010). Detailed electrophysiologic and functional neuroimaging studies on the emotion of fear have revealed that interactions between the amygdala and hippocampus in the limbic system and the ventromedial prefrontal cortex (VMPFC) and dorsolateral prefrontal cortex (DLPFC) support the acquisition, storage, retrieval, and regulation of emotional memory (Sotres-Bayon, Cain et al. 2006; Hartley and Phelps 2010).

2.3 Stimulation of dorsolateral prefrontal cortex (DLPFC) and prefrontal-limbic circuit plasticity

A primary goal of cognitive therapy is to enable the patient to more accurately assess a situation, using cognitive strategies such as emotional reappraisal, selective attention and reframing (Gross 1998; Gross and John 1998), in order to regulate the associated emotional responses (Allen, McHugh et al. 2008). In turn, successful treatment of emotional dysregulation (altering the emotional response) after TBI involves the employment of cognitive strategies that require the patient's active engagement and cognitive reappraisal of the event (Olsson and Ochsner 2008; Macnamara, Ochsner et al. 2010). Functional neuroimaging studies on reappraisal of negative affect have consistently reported increased activation of the DLPFC and/or VLPFC and decreased amygdala activation (Wager, Davidson et al. 2008; Ochsner, Hughes et al. 2009; McRae, Hughes et al. 2010). The cognitive regulation of emotion model (Ochsner, Bunge et al. 2002; Delgado, Nearing et al. 2008; Schiller and Delgado 2010) proposes that the DLPFC is involved in the effortful manipulation or interpretation of the emotional stimulus and the VLPFC may have a function in the selection of emotional interpretation (Wager, Davidson et al. 2008). The changes observed in the amygdala are thought to result from top-down modulation of the emotional meaning of the stimulus.

However, patients with TBI show reduced responsiveness to these cognitive strategies (McDonald, Bornhofen et al. 2009). It is possible that stimulation of the residual prefrontal-limbic circuits may increase the efficacy of cognitive interventions for emotional regulation post-TBI. Transcranial magnetic stimulation (TMS) and transcranial direct current stimulation (tDCS), particularly anodal tDCS, have been shown to increase excitability and induce long-lasting changes in motor (Bolognini, Pascual-Leone et al. 2009; Edwards, Krebs et al. 2009; Reis, Schambra et al. 2009) and cognitive systems (Minussi, Cappa et al. 2008). In one study that used cranial electrotherapy for emotional control post-TBI, improvement was seen on all negative mood factors on the Profile Of Mood States on pre-post analysis with alternating current cranial electrotherapy compared with sham-treated and placebo controls, with good tolerance and no significant adverse effects (Smith, Tiberi et al. 1994). TDCS is promising as a relatively simple, non-invasive and safe modality to probe the mechanisms behind cognitive regulation of emotion and investigate whether increasing excitability in prefrontal-limbic pathways, that show reduced excitability post-TBI, will enhance the responsiveness of patients to cognitive strategies that mediate emotional regulation.

The rationale for neuromodulatory effects of tDCS is that at the cellular level, the effect of applied electricity can be considered on three levels (Gross 2007). The applied electric currents may (1) change the electrical state of neurons by triggering or blocking action potentials; (2) change neurotransmitter (e.g. glutamate, dopamine, serotonin) activity or neuromodulator (e.g. endogenous opioids) levels; (3) alter electrical activity within neuronal circuits and networks (e.g., in the complex “mood/affects/emotion regulating” network). All devices delivering non-invasive electrical brain stimulation consist of two components: a unit generating the current and at least two electrodes that enable the current to enter and to leave the brain. The clinical effects of brain stimulation depend on the dose of electricity delivered to the brain and on brain structures that are targeted (Kleiman 2004).

2.4 We will use resting state functional connectivity MRI (fMRI) to directly test the hypothesis that tDCS strengthens fronto-limbic connections involved in emotional processing. Resting state functional connectivity MRI (fMRI) is a recently evolving method from which functional connectivity between distant brain regions is extracted based on low-frequency fluctuations. It allows for the identification of discrete functional networks in the brain. Distributed networks of brains regions have been shown to display temporally correlated patterns of spontaneous activation. This temporal coherence tends to occur in the brain regions that are anatomically connected (Zhang and Raichle 2010). Furthermore, functionally connected networks derived using resting state approaches mirror activation patterns found in task-based functional imaging studies. For clinical purposes, the strength and nature of network connections can be compared in clinical and healthy populations, or resting state can be used in a repeated measures fashion to assess changes within clinical groups. Resting state fMRI had been employed in a small number of studies of TBI patients to examine how network connectivity changes with recovery (Nakamura, Hillary et al. 2009; Hillary, Slocomb et al. 2011).

3. Study Design.

Forty (40) individuals status post TBI with complaints of emotional dysfunction 6 months post-brain injury and twenty-five (25) healthy controls will participate in the study. We expect a

total of 65 subjects to enroll. After obtaining informed consent, they will be screened to ensure that they meet inclusion-exclusion criteria at Visit 1. At visit 1 subjects also will be tested on chemosensory performance evaluation using Sniffin' sticks test and oculomotor movement evaluation using King-Devick test Subjects meeting criteria will then be tested at baseline on neuropsychological assessments, tests of attention (at Visit 2), and the emotional function battery (at Visit 3). The TBI subjects will also undergo resting-state MRI (at Visit 4).

There will be a total of 4 testing visits (visits 1, 2 3 and 4 as described above) prior to starting the study, after which, subjects will receive treatment for visits 5-16). After completion of treatment, the subjects will then be re-tested on the baseline assessments and resting state MRI (Post-intervention Visits 17, 18, 19 and 20the total amount of visits for TBI subjects will be 20.). Healthy Control Subjects will have a total of three testing visits (1-3) only.

The subjects with TBI will then be randomly assigned to one of two groups, each consisting of 10 subjects. Subjects will be randomized by a simple randomization method. They will have a 50/50 chance of being in either group by flipping of a coin. Randomization will be carried out by the PI. Subjects and study personnel performing assessments and data analysis will be blind to group assignment. Only the PI will be unblinded.

The experimental group will receive active tDCS for 20 minutes and computerized cognitive training twice a week for 30-45 minutes for 6 weeks as described below. The control group will receive sham-tDCS 20 minutes and computerized cognitive training for 30-45 minutes twice a week for 6 weeks (12 training sessions). The sham group will not receive real tDCS after completion of the study.

In addition, we will conduct a qualitative interview with each of the subjects. Giorgi's phenomenology (Giorgi 1985; Kleiman 2004) is the method that will be used to describe the experiences of persons undergoing tDCS for treatment of TBI. In-person audio-taped interviews will be conducted at the completion visit by an experienced qualitative interviewer and immediately transcribed verbatim. Interviews are expected to range from 30 minutes to 1 hour. Each of the subjects will be asked the open-ended question, "Please tell me about your experience undergoing tDCS for the treatment of traumatic brain injury." Probes included the following questions: "What was the experience like for you? What should we continue to do and what should we change to make the experience better for patients?" Themes will be derived using the constant comparative method (Sandelowski 1995; Thorne 2000).

II. CHARACTERSTICS OF THE RESEARCH POPULATION

1. Number of Subjects. Forty (40) patients with complaints of emotional dysfunction 6 months post-brain injury between 18 and 85 years of age, and twenty-five (25) healthy control subjects will participate. The patients will be referred after discharge from the inpatient brain injury units of Bellevue Hospital and Hospital for Joint Diseases and from their outpatient TBI clinics, and will meet the inclusion-exclusion criteria listed below.

- 2. Gender of Subjects.** Both male and female subjects will be included. We will attempt to recruit 50% of male and 50% female subjects. There will be no gender based enrollment restrictions.
- 3. Age of Subjects.** The age range of subjects is between 18 and 85 years. The goal of this study is to understand emotional dysfunction in adult patients. Individuals below the age of 18 will be excluded from this study since pediatric TBI is relatively rare and the mechanisms of recovery may differ. Adults over 85 will be excluded to rule out possible confound of co-morbid medical conditions.
- 4. Racial and Ethnic Origin.** There are no exclusions based on gender or ethnic group.
- 5. Inclusion Criteria.**
 - (1) Brain Injury at least 6 months prior.
 - (2) Family or self-identification of cognitive or emotional difficulties.
 - (3) Unchanged and stabilized medical treatment in the three weeks prior to the screening.
- 6. Exclusion Criteria.**
 - (1) Any social or medical problem that precludes completion of the protocol.
 - (2) Presence of focal motor deficits in the upper extremities.
 - (3) Comorbid psychiatric disease such as schizophrenia, or active substance abusers (except nicotine).
 - (4) History of craniectomy, active infection, or seizure activity beyond 1 week post-TBI.
 - (5) Complicating medical problems such as uncontrolled hypertension, diabetes with signs of neuropathy, and previous neurological illness such as head trauma, prior stroke, epilepsy or demyelinating disease, implanted neuromodulatory or electronic device, metal in head
 - (6) Pregnancy
- 7. Vulnerable Subjects.** Although TBI patients have some cognitive impairment, we will only consent patients who have been determined to have the capacity to give consent. This determination will be made by [name], [name] Im or [name] who are specialists in Brain Injury and will screen patients to determine if they are in a stable cognitive state, whose capacity to give consent is not expected to fluctuate. Only such patients will be enrolled in the study. We will provide information to the subjects in terms that they can fully understand, and capacity to consent will be determined by the subject's verbal understanding of the protocol as determined by the PI. We will not exert any overt or covert coercion, and no financial incentive will be offered. The consent document that each potential subject will be asked to sign will be written in the language that he or she understands, and will be approved by the IRB.

III. METHODS AND PROCEDURES

1. Methods and Procedures.

Patients will sign informed consent and be required to undergo self-assessment (using the TIRR symptom checklist), caregiver assessment (using the Neurobehavioral Functioning Inventory/NFI), and clinician assessment (using NRS-R) to determine neurobehavioral status on study entry. Screening procedures will also include medical history and interview, review of medications and imaging records to ensure that participants meet inclusion/exclusion criteria. Screening procedures will take place at the Motor Recovery Laboratory. The following outcome measures will be administered at baseline and at the end of the 6-week tDCS intervention.

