1.5 Intervention with active and sham tDCS and computerized cognitive re-training

After providing informed consent approved by the IRB of New York University School of Medicine (NYUSoM), all patients will undergo testing with the above listed outcome measures. They will then be randomized into the two intervention groups, the groups being (1) tDCS + cognitive re-training, and (2) sham tDCS + cognitive re-training. The intervention will be carried out for 20 minutes twice a week for 6 weeks during which the subjects in each group will be engaged in re-training using visual cognitive re-training software programs for 30-45 minutes during each session (www.positscience.com). These re-training programs have been used in patients with TBI and have been shown to be effective (Fisk, Novack et al. 2002; Calvanio, Williams et al. 2004; Novack, Banos et al. 2006). Cognitive re-training will thus be individualized to each patient's cognitive level, but still be systematic, and will not need direct one-on-one supervision by a neuropsychologist.

Transcranial direct current stimulation will be delivered by trained study personnel using the saline-soaked pair of surface sponge electrodes (35 cm²) delivered by a specially developed, battery-driven, constant direct current stimulator (Fisher Wallace Cranial Stimulator, Fisher Wallace Laboratories, New York) with a maximum output of 4 mA (**Fig. 1**). FDA approval: The Cranial Stimulator is an FDA cleared device indicated for application of electrical stimulation to a patient's head to treat insomnia, depression, or anxiety. TBI subjects experience insomnia, depression and anxiety and all subjects enrolled in this study will have some combination of these problems. The purpose of this study is to understand the mechanisms behind the depression, anxiety and insomnia that patients with TBI experience. The hypothesis is that emotional dysregulation contributes to the symptoms. This device will therefore be used in alignment with FDA clearance indications. To stimulate the DLPFC, the anode electrode will be placed over F3 according to the 10-20 international system for EEG electrode placement (Fregni, Boggio et al. 2005) (**Fig.2**). The cathode will be placed over the contralateral supraorbital area.

Fig.1. FDA approved Fisher Wallace Cranial Stimulator.

[figure not shown]

Fig.2. Placement of electrodes (Rosa and Lisanby 2012).

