We will focus our investigations on the left DLPFC, as modulation of this area by tDCS has been shown to enhance working memory (Fregni, Boggio et al. 2005) which also demands similar attentional resources as emotional control (Anderson and Knight 2010). A constant current of 2 mA intensity will be applied for 20 min. Patients will feel the current as an itching sensation at both electrodes at the beginning of the stimulation. For sham stimulation, the electrodes will be placed in the same position; however, the stimulator will be turned off after 5 seconds (Siebner, Lang et al. 2004) so that patients will feel the initial itching sensation in the beginning, but receive no current for the rest of the stimulation period; this procedure has

been used to blind patients to the stimulation condition (Nitsche, Liebetanz et al. 2003; Nitsche, Schauenburg et al. 2003).

2. Data Analysis and Data Monitoring.

Power Analysis: This is a pilot feasibility study hence sample size is small and arbitrary. Power analysis from these pilot data will be used to determine sample size in future studies. Subjects with TBI will be randomized to the 2 treatment groups n=10 in each group.

Data Analysis:

1) To examine the relationship between alerting, orienting and executive attention and emotional recognition, reactivity and regulation in patients with TBI and controls.

Hypothesis: Patients with TBI will show clear patterns of attentional and emotional impairment compared with controls. Deficits in executive attention will be related to deficits in emotional appraisal in patients.

Scoring of emotional recognition, reactivity and regulation:

- 1) **Emotional reactivity film clips:** Physiological responses (cardiac inter-beat, finger pulse amplitude, finger pulse transmission time, ear pulse transmission time, and respiration period) will be recorded, and input from baseline will be subtracted from input across the most intense segment of the clip. Data will be combined into a single aggregate score for each diagnostic group to increase reliability and reduce noise; aggregate scores of patients and controls will then be compared. Facial behavior will be recorded and coded for displays of the target emotion across the most intense segment of the clip; data from patients and controls will then be compared.

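### The protocol counts 40 TBI subjects but randomises two groups of 10, and nothing in the available text says how 40 becomes 20

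*Protocol*

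**What the plan says.** Two counts of TBI subjects appear, each of them twice.

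- **Forty.** Section I.3 (Study Design) plans for "Forty (40) individuals status post TBI with complaints of emotional dysfunction 6 months post-brain injury and twenty-five (25) healthy controls" and expects a "total of 65 subjects to enroll". Section II.1 (Number of Subjects) repeats "Forty (40) patients with complaints of emotional dysfunction 6 months post-brain injury".
- **Twenty.** The randomisation paragraph of I.3 says: "The subjects with TBI will then be randomly assigned to one of two groups, each consisting of 10 subjects". The power paragraph of III.2 says: "Subjects with TBI will be randomized to the 2 treatment groups n=10 in each group".

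Four further statements bear on how the two counts relate:

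- Section I.3 puts screening after consent: "After obtaining informed consent, they will be screened to ensure that they meet inclusion-exclusion criteria at Visit 1". Only those who meet the criteria go on to baseline testing.
- Section II.1 says of the 40 that they were referred "and will meet the inclusion-exclusion criteria listed below".
- Section III.1.5 says that "all patients will undergo testing with the above listed outcome measures. They will then be randomized into the two intervention groups".
- Section I.3 gives TBI subjects one schedule of 20 visits: testing at 1-4, treatment at 5-16 and re-testing at 17-20. Only healthy controls stop early, after visit 3.

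Allocation is by coin flip. The power paragraph calls this a pilot with a small, arbitrarily chosen sample and gives no alpha, power, effect size or dropout rate. Section III.2 intends the Aim 2 results to size later trials.

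**The concern.** The number randomised is a basic figure of the trial, and here it has two incompatible values. Ten per group is the only randomised size written down. Forty randomised is an inference, but the text leads to it: 40 patients take part, they meet the criteria, all are tested, and they are then randomised.

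The meaning of 40 is also unclear. The order of events in I.3 suggests a count at consent, before screening. The wording of II.1 suggests a count after screening.

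The randomised number sets the precision of Aim 2 (attention and emotional regulation) and Aim 3 (connectivity), and of the estimates meant for planning the next trial. It also sets how many people receive active or sham stimulation and when randomisation stops. Aim 1 needs no randomisation, but its TBI sample still depends on what 40 means. If only some TBI subjects are to be randomised, the protocol gives no rule for choosing them.

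**Working it through.** **1. The plan's own totals.** 40 + 25 = 65, which reproduces the stated enrolment, so 40 is deliberate. 2 × 10 = 20, which does not reproduce 40. The gap is 20 subjects.

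**2. Loss needed to reconcile them.** 1 − 20/40 = 50% before randomisation. Starting from 20 and inflating by 20/(1 − d) gives 23, 25, 29 and 40 enrolled for d = 10%, 20%, 30% and 50%. Only 50% reaches 40, and the protocol states no rate.

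**3. Precision for Aim 2.** For two groups and two time points, the test of differential change is a two-sample comparison of change scores. With n per group, in units of the SD of change:

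- SE = √(2/n)
- 95% half-width = t(0.975, 2n − 2) × SE

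The loss rates below are assumed.

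| Loss from 40 | Randomised | n per group | SE | Half-width |
|---|---|---|---|---|
| 0% | 40 | 20 | 0.316 | 0.64 |
| 10% | 36 | 18 | 0.333 | 0.68 |
| 20% | 32 | 16 | 0.354 | 0.72 |
| 30% | 28 | 14 | 0.378 | 0.78 |
| 40% | 24 | 12 | 0.408 | 0.85 |
| 50% | 20 | 10 | 0.447 | 0.94 |

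The ratio of the extremes is 0.447/0.316 = 1.41, so the SE is 41% larger with 20 randomised than with 40.

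**4. Would ordinary attrition explain 20?** Suppose exactly 40 consent and each is lost independently with probability d. The number randomised is then Binomial(40, 1 − d). The chance that 20 or fewer remain is 0.002% at d = 20%, 0.6% at 30%, 13% at 40% and 56% at 50%. This does not apply if recruitment simply stops once 20 are randomised, but the protocol states no such stop.

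**5. Aim 1.** The 95% half-width for a correlation near zero is tanh(1.96/√(n − 3)): 0.31 with 40 TBI subjects and 0.44 with 20.

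**6. Fixed group sizes under a coin flip.** With 20 subjects, an exact 10:10 split has probability C(20,10)/2²⁰ = 17.6%, and both groups lie within 6-14 with probability 95.9%. With 40 subjects, an exact 20:20 split has probability 12.5%, and both groups lie within 14-26 with probability 96.2%. Neither 10 nor 20 per group can be promised under this method.

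**The case against.** The strongest reply is that the protocol is explicit about the randomised size: 10 per group, in two places, consistently. The figure 40 goes with taking part and enrolling. Loss before randomisation is foreseen: screening follows consent, one exclusion covers problems that would prevent completion, a metal questionnaire precedes the MRI, and the risk section allows withdrawal. On this view only the size of the loss is unstated. The study is also a pilot with an admittedly arbitrary sample. No power claim rests on the number, and the planned analyses run at either size.

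Part of this stands. It is wrong to say that every one of the 40 must reach randomisation; the accurate statement is that the protocol names no TBI subgroup that is not randomised. The precision loss applies only if 40 were meant to be randomised. A block of text before the item on the consent process is missing from the public copy, so the absence of a bridge can be asserted only for the text available.

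The contradiction remains. Section II.1 says that the 40 meet the criteria, which conflicts with a count taken before screening. Being a pilot excuses the lack of a power calculation, but not two different counts. A split of 40 for Aim 1 and 20 for Aims 2 and 3 is plausible, but it is written nowhere. Nor can this be left to an analysis plan, because the protocol does state the number and states it inconsistently.

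**Conclusion.** The concern holds and needs correcting. The stated 40 TBI subjects and the stated 2 × 10 randomised differ by 20, and nothing in the available text reconciles them. Agreement would require a 50% loss before randomisation that the protocol does not mention.

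Depending on the reading, the half-width for the between-group difference in change runs from 0.64 to 0.94 SD of change. This assumes normal changes, equal SDs, equal groups and complete data. The documents do not show which count is intended, so this range measures the ambiguity and is not a demonstrated loss of precision. Separately, the fixed size of 10 per group does not fit allocation by coin flip.

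**What to change.** Align sections I.3, II.1, III.1.5 and the power paragraph of III.2 on one randomised number, and say whether 40 means consented, eligible or randomised. Which number is right is for the sponsor to state. The wording follows from the answer:

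- **All 40 are randomised.** State about 20 per group in I.3 and III.2.
- **Twenty are randomised and the others give baseline data for Aim 1 only.** Say so, state how the 20 are chosen, and limit the 20-visit schedule in I.3 and the post-testing payment (Payment for Participation) to those 20.
- **Forty consent, to yield 20 randomised.** State this and the assumed loss, and correct II.1, which describes all 40 as meeting the criteria.

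In each case, describe the group sizes as expected. Simple randomisation can stay.

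The cost is a wording amendment if the text is aligned to the number already intended. It rises only if 10 per group is the operative plan and the sponsor chooses 20 per group instead. That adds 20 treated subjects: 20 × 12 = 240 treatment visits and 20 × 4 = 80 post-intervention visits including MRI. If 40 had been the consented number, it would also need 20 × 4 = 80 more baseline visits for those 20, and 20/0.5 = 40 more consents at the same 50% loss.
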